10.1 Mortality

The number and cause of death will be reported and summarized by treatment arm.

10.2 Hb-related Safety Endpoints

Hb-related safety endpoints will be defined using data from the central laboratory. The analyses will use all central laboratory values in the database starting from randomization. No imputation will be performed for missing data.

Any post-baseline Hb value above a set threshold will be considered as a “yes” in the Hb related safety analysis. Subjects with no available post-baseline data will be excluded from this analysis. All other subjects will be classified to the “no” category.

The number and proportion of subjects with at least 1 of the following criteria at any post-baseline time point will be summarized by analysis time period. The denominator for calculating proportion is the total number of subjects with available post-baseline Hb values in each analysis time period. A 95% confidence interval of the proportion will be performed by treatment group using the Clopper-Pearson exact method [[Clopper, 1934](#)].

- Hb > 11.0 g/dL for US.
- Hb > 12.0 g/dL.
- Hb > 13.0 g/dL.
- Hb > 14.0 g/dL.
- Hb increase > 1.0 g/dL within any 2-week interval.
- Hb increase > 2.0 g/dL within any 4-week interval.
- Hb < 8.0 g/dL.
- Hb < 9.0 g/dL.

A Mantel-Haenszel estimation of risk difference stratified by the baseline strata will be conducted, and the corresponding 2-sided 95% confidence interval of the risk difference will be calculated. The associated odds ratio and corresponding 2-sided 95% confidence interval will also be calculated.

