**Trial Duration:**

Each subject in this trial is expected to participate in the following periods of the trial (approximate durations listed):

[figure not shown]
- Two Screening Visits (Screening Visit 1 and Screening Visit 2) (Weeks -8 to 0)
- Baseline/Randomization Visit (Week 0/Day 1)
- Treatment Period (Conversion and Maintenance) Trial Visits/Evaluations while receiving IMP: Weeks 2, 4, 6, 8, 10, 12, ( $\pm 3$  days) 16, 20, 24, ( $\pm 5$  days), 26 ( $\pm 3$  days), 30, 34, 38, 42, 46, 50, ( $\pm 5$  days) 52/EOT ( $\pm 3$  days).
- ET Visit (+ 7 days)
- Follow-up Visit/EOT (4 weeks after the ET [+ 7 days] visit).
- Unscheduled visit(s)

**Trial Completion:** The trial will be considered completed after all randomized subjects have completed their final trial visit (ET, Week 52/EOT, or Safety Follow-up).

**Subject Completion:** A subject will be considered as having completed the trial after completion of their final trial visit (ET or Week 52/EOT). Safety Follow-up Visit data summarization and analysis will be performed separately.

The trial duration for an individual subject from the time the informed consent form (ICF) is signed to the final subject assessment is expected to be approximately 64 weeks.

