The starting dose of vadadustat for the high darbepoetin alfa group TIW arm will be 750 mg and for the low darbepoetin alfa TIW arm will be 600 mg. In the ongoing global phase 3 program, subjects are getting higher total weekly doses as subjects treated in the high darbepoetin alfa group may be administered 600 mg vadadustat daily for a total weekly dose of 4200 mg; no significant dose-related safety concerns have been identified by the Independent Data Monitoring Committee (IDMC) in these trials.

Assessment of animal-to-human safety margins is presented in the IB.

Intensive Hb monitoring, a strict dose adjustment algorithm, and phlebotomy will be implemented to mitigate the potential risk of a rapid Hb rise, as follows:

- Hb measurements are scheduled at least every 2 weeks to Week 20.
- The dose adjustment algorithm will target a narrow Hb range, 10.0 to 11.0 g/dL in the US and 10 to 12 g/dL in Europe.

- The protocol specifies that phlebotomy may be considered in the setting of high Hb levels ( $> 14.0$  g/dL) or a high Hb rate of rise, based on the investigator's judgment.

Phase 2 studies demonstrated that cessation of treatment resulted in prompt reduction in mean Hb within 2 to 4 weeks.

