### **Unscheduled Visits**

Unscheduled assessments may be conducted at any time as medically warranted. At minimum, the following activities/procedures will be performed.

- Adverse Event assessments.
- Major adverse cardiovascular events (MACE) assessment.
- Any other procedures that are medically warranted at the discretion of the investigator.

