#### **9.4.2.2 Remaining Safety Endpoints**

The analysis of the safety endpoints will be detailed in the SAP.

Any Hb value postdose above a set threshold will be considered as a “yes” in the Hb related safety analysis. Subjects with no available data post Baseline will be excluded from this analysis. All other subjects will be classified to the “no” category.

The analysis of proportion of subjects with any Hb increase  $> 1.0$  g/dL within any 2-week interval or  $> 2.0$  g/dL within any 4-week interval post Baseline will classify a subject as a “yes” if at least 1 of the following criteria at any point after Day 1 is met:

- Hb increase  $> 1.0$  g/dL within any 2-week interval.
- Hb increase  $> 2.0$  g/dL within any 4-week interval.

Subjects with no available data post Baseline will be excluded from this analysis. All other subjects will be classified to the “no” category.

Observed values of continuous and categorical parameters and changes from Baseline for continuous parameters to each trial visit will be summarized descriptively for vital signs and clinical laboratory results. Graphical displays of selected laboratory parameters will also be provided.

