5.1 Visit and Analysis Time Period Classification

The time windows in this section reflect the administrative range around each visit for analysis. They are wider than those stated in the protocol to reduce missing values by capturing as many observation dates as possible. [Table 1](#). provides the convention to classify assessment dates into protocol-defined visits and analysis time periods for assessments conducted at every visit, such as Hb value.

Unless otherwise specified, all assessments will be mapped to visit windows based on the date of the assessment relative to the first dose date, regardless of subject disposition or the CRF page completed, e.g., “Unscheduled”, “End of Treatment”, etc. Similarly, all values collected within a reporting period will be considered for identification of safety events of interest.

If more than 1 Hb value is available in an analysis time period post-baseline, the average of all observed values (at most 1 per day) will be assigned to that period. For example, the

window for the primary efficacy outcome, analysis time period 3, includes any Hb value (at most 1 per day) assessed between Study Days 127 to 196, corresponding to Weeks 20, 24 and 26.

Efficacy evaluations will use Hb values as assessed by the central laboratory.

When more than 1 assessment is made for other measures (not Hb) within a given visit window post-baseline, the value of the assessment closest to the end of the window is the value associated with that visit for summaries over time. Most summaries of results by visit (e.g., laboratory or vital sign results) will use the single value for each visit determined by this convention. Notable exceptions to this convention are the primary efficacy outcome and clinically significant changes.

If no assessment is available within a time window, then the associated visit and week classifications will be missing.

Table 1. Classification of Assessments at Every Visit

Time Period	Visit/Week	Target Day	Actual Study Day of Visit
Baseline	Screening Visit 1	-	-
	Screening Visit 2	-	-
	Baseline Visit	Day 1	Day 1 (first dose date) ^a
1) Weeks 2-8	Week 2	Day 14	Day 2-21
	Week 4	Day 28	Day 22-35
	Week 6	Day 42	Day 36-49
	Week 8	Day 56	Day 50-63
2) Weeks 10-16	Week 10	Day 70	Day 64-77
	Week 12	Day 84	Day 78-98
	Week 16	Day 112	Day 99-126
3) Primary Efficacy Period (PEP) (Weeks 20-26)	Week 20	Day 140	Day 127-154
	Week 24	Day 168	Day 155-175
	Week 26	Day 182	Day 176-196
4) Weeks 30-42	Week 30	Day 210	Day 197-224

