14.3.5.5.1.1	Change from Baseline in Laboratory Test Results by Visit -- Lipids (Conventional Unit)	Safety Population

Table Number	Table Title	Population
14.3.5.5.1.2	Change from Baseline in Laboratory Test Results by Visit -- Lipids (SI Unit)	Safety Population
14.3.5.5.2.1	Percent Change from Baseline in Laboratory Test Results by Visit -- Lipids (Conventional Unit)	Safety Population
14.3.5.5.2.2	Percent Change from Baseline in Laboratory Test Results by Visit -- Lipids (SI Unit)	Safety Population
14.3.5.6.1.1	Change from Baseline in Laboratory Test Results by Visit -- C-reactive protein, Vascular Endothelial Growth Factor and Hepcidin (Conventional Unit)	Safety Population
14.3.5.6.1.2	Change from Baseline in Laboratory Test Results by Visit -- C-reactive protein, Vascular Endothelial Growth Factor and Hepcidin (SI Unit)	Safety Population
14.3.5.6.2.1	Percent Change from Baseline in Laboratory Test Results by Visit -- C-reactive protein, Vascular Endothelial Growth Factor and Hepcidin (Conventional Unit)	Safety Population
14.3.5.6.2.2	Percent Change from Baseline in Laboratory Test Results by Visit -- C-reactive protein, Vascular Endothelial Growth Factor and Hepcidin (SI Unit)	Safety Population
14.3.5.7.1	Change from Baseline in Laboratory Test Results by Visit -- Erythropoietin and Reticulocytes (Conventional Unit)	Safety Population
14.3.5.7.2	Change from Baseline in Laboratory Test Results by Visit -- Erythropoietin and Reticulocytes (SI Unit)	Safety Population
14.3.5.8.1	Cumulative Number (%) of Subjects with Abnormal Laboratory Test Results -- Potential Liver Injury	Safety Population

Table Number	Table Title	Population
14.3.5.8.2	Number (%) of Subjects with Abnormal Laboratory Test Results -- Liver Function and Potassium	Safety Population
14.3.5.9	Hemoglobin (Hb)-Related Safety Endpoints	Safety Population
14.3.6.1	Change from Baseline in Vital Signs and Body Weight by Visit	Safety Population
14.3.6.2	Number (%) of Subjects with Abnormal Findings in Vital Signs	Safety Population
14.3.7.1	Change from Baseline in ECG by Visit	Safety Population
14.3.7.2	Number (%) of Subjects with Abnormal Findings in ECG	Safety Population
14.3.8.1	Summary of Dialysis History and Details	Safety Population
14.3.8.2	Summary of Dialysis Adequacy	Safety Population
14.3.9	Summary of Special Situations	Safety Population

Listing Number	Listing Title	Population
16.2.1.1	Informed Consent	Randomized Population
16.2.1.2	Subject Disposition	Randomized Population

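### In Weeks 30-42 the row for a 2-week Hb rise > 1.0 g/dL will read near zero because routine visits are 4 weeks apart, whatever the true rate of rapid rises

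*SAP*

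**What the plan says.** SAP Section 10.2 lists eight Hb safety criteria, to be summarised by analysis time period. One is "Hb increase > 1.0 g/dL within any 2-week interval"; the 4-week rise of more than 2.0 g/dL is a separate line. On who is counted, "The denominator for calculating proportion is the total number of subjects with available post-baseline Hb values in each analysis time period". Each proportion gets a Clopper-Pearson interval, and a Mantel-Haenszel risk difference and an odds ratio follow. Missing values are not imputed.

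The default to *no* appears in both documents. SAP Section 10.2 words it around the Hb thresholds. Protocol Section 9.4.2.2 states it for the rise endpoint itself: "Subjects with no available data post Baseline will be excluded from this analysis", and all remaining subjects are a *no*. Neither document requires a subject to have two values close enough together to show a 2-week rise.

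The visit list in the Protocol synopsis (Trial Duration) places the later visits at Weeks "30, 34, 38, 42, 46, 50", each with a window of 5 days either side. SAP Table 1 assigns Weeks 30 to 42 (Study Days 197 to 308) to analysis period 4.

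Two further provisions bear on the row. SAP Section 5.1 says that "all values collected within a reporting period will be considered for identification of safety events of interest", whatever form they were recorded on. Protocol Section 8 says: "Unscheduled assessments may be conducted at any time as medically warranted".

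**The concern.** A 2-week rise can be seen only in a subject with two Hb values about 14 days apart or less. The planned denominator ignores that requirement. In a period with 4-weekly visits, nearly everyone is counted as having had no rapid rise when in fact nobody looked.

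Rapid Hb rise is a named safety endpoint and a trigger for reducing or interrupting the dose. A near-zero rate with a short interval, printed beside usable rates from Weeks 2-8, invites the conclusion that rapid rises stop once conversion is complete. The plan's data cannot support that conclusion for Weeks 30-42.

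**Working it through.** The documents give no expected rate for this row, so there is no stated figure to reproduce. The check is arithmetic on the schedule.

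**Inputs.** Visit weeks and windows come from the Protocol synopsis: Week 26 is plus or minus 3 days, and Weeks 30, 34, 38, 42 and 46 are plus or minus 5 days. The analysis periods come from SAP Table 1.

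**Shortest and longest in-window gaps** (nominal gap minus or plus both windows):

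| Pair | Nominal (days) | Shortest | Longest |
|---|---|---|---|
| Week 26 to 30 | 28 | 28 - 3 - 5 = 20 | 28 + 3 + 5 = 36 |
| Weeks 30-34, 34-38, 38-42 | 28 | 28 - 5 - 5 = 18 | 28 + 5 + 5 = 38 |
| Week 42 to 46 | 28 | 28 - 5 - 5 = 18 | 28 + 5 + 5 = 38 |

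The shortest is 18 days. No in-window pair qualifies under a strict 14-day reading, or under any tolerance up to 17 days. It does not matter whether a pair that crosses a period boundary is assigned by its earlier or later visit. A fully observed subject still has four Hb values in the period and is counted as a *no*.

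**Nominal 2-week intervals by period**, assigned to the later visit: Weeks 2-8 have 4, Weeks 10-16 have 2, the primary efficacy period has 1 (24-26), Weeks 30-42 have 0 and the secondary efficacy period has 1 (50-52). The total is 8 of 17 intervals.

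**What the row prints with no events.** The Clopper-Pearson upper limit for 0 of n is 1 - 0.025^(1/n).

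- n = 100: 1 - 0.025^(1/100) = 3.6%.
- n = 70 (100 less the planned 30% dropout): 1 - 0.025^(1/70) = 5.1%.

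With zero events in both arms the risk difference is zero and the odds ratio is undefined.

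**Values that can give a *yes*.**

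- Early Termination: the Schedule of Assessments has a CBC at this visit, due within 7 days of stopping IMP. If 30% dropout is spread at a constant hazard over 364 days (an assumption), the share of subjects at risk who terminate during the 112 days of the period is 1 - 0.7^(112/364) = 10.4%. Not all of those draws fall within 14 days of the last visit.
- Out-of-window visits: SAP Table 1 windows are adjacent (Week 30 ends on Day 224 and Week 34 starts on Day 225), so a late visit and an early one can be close together.
- Unscheduled central draws.

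The documents give no rate for these. Assume that 5% to 20% of subjects have such a pair and that 5% to 15% of those pairs show the rise. The row is then 0.05 x 0.05 = 0.25% to 0.20 x 0.15 = 3%. At 40% of subjects and 15% of pairs it would be 6%.

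**The efficacy periods.** The one 2-week interval in each (24-26 and 50-52) can be 14 - 5 - 3 = 6 to 14 + 5 + 3 = 22 days long. If visit days are uniform within their windows (an assumption), there are 11 x 7 = 77 day combinations, of which 42 give a gap of 14 days or less: 42/77 = 54.5%. These rows can be observed, but under a strict 14-day rule for only about half the subjects.

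**The case against.** The strongest case against has four parts.

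**Scheduled data can give a *yes*.** A reader might infer that the row must be exactly zero, or that only unscheduled draws can contribute. The documents do not support that. The Early Termination CBC is a scheduled assessment, SAP Section 5.1 classifies values by date, and out-of-window visits count too. The claim is therefore limited to routine on-treatment visits, and the row is near zero rather than necessarily zero.

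**Other results give cover.** Protocol Section 9.4.2.2 classes a subject as a *yes* if either rise criterion is met at any point after Day 1. That trial-level result draws on all eight 2-week intervals and on the 4-week criterion. The 4-week row remains usable in Weeks 30-42: in a simulation of 100,000 subjects with visit days uniform within windows, 99.9% had a pair 28 days or less apart. A US subject at 10.0 to 11.0 g/dL who rises by more than 1.0 must pass 11.0, and is caught by that threshold row if still above it at a draw. This stands, but the cover is partial. A rise of 1.2 in 2 weeks and 0.3 in the next 2 is 1.5 over 4 weeks and meets neither rise row at 4-weekly visits. A European subject going from 10.5 to 11.7 does not cross 12.0, and a US subject going from 9.5 to 10.7 does not cross 11.0.

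**Little depends on it.** Most safety analysis is descriptive and the row is outside the testing hierarchy in SAP Section 9.5. That stands and sets the priority. A reader might also infer bias between arms. The visit schedule is identical in all arms, so the schedule itself produces none. What remains is that any difference in this row would come from the irregular values, whose timing may vary by arm in an open-label trial.

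**The number of missed rises is unknown.** A constant, independent risk of 0.5% to 5% per 2-week interval would give 3.9% to 33.7% of subjects with a rise over the eight intervals from Week 26 to 42, using 1 - (1 - q)^8. It is tempting to present that as the shortfall, but those risks are assumptions and no document supports any value in the range.

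Protocol Section 4.3 says "Hb measurements are scheduled at least every 2 weeks to Week 20", whereas the visit list has no Week 14 or 18. That is a separate wording point. It stops at Week 20 and adds nothing here.

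**Conclusion.** The concern holds for one block of one descriptive table. As written, the Weeks 30-42 entry for the 2-week rise will show a near-zero proportion, with an upper limit of 3.6% (100 subjects) or 5.1% (70 subjects) if there are no events, and a risk difference that carries almost no information. The cause is the visit schedule combined with a denominator that needs only one value. The entry is no evidence that rapid rises are absent.

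This rests on visits being kept within protocol windows and on an allowed gap below 18 days. From 18 days upward some in-window pairs would begin to qualify. The primary and key secondary analyses, the threshold rows and the trial-level rise endpoint are not put in doubt. Worth correcting, at low priority.

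**What to change.** In SAP Section 10.2 and Table 14.3.5.9:

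1. State the allowed gap in days for the 2-week criterion: 14, or 14 plus a stated tolerance that stays below 18.
2. For each period, print the number of subjects with at least one qualifying pair beside the planned denominator.
3. For Weeks 30-42, print *not evaluable by schedule* with the count of events from Early Termination, unscheduled and out-of-window values. Give no percentage, confidence interval, risk difference or odds ratio.
4. In the other periods keep the planned denominator. A proportion among subjects with a qualifying pair may be added as supplementary only. It selects on sampling after randomisation: subjects with a medically warranted or termination draw enter preferentially, and in the efficacy periods only about 55% of subjects would remain under a strict 14-day rule with uniform visit days.

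The cost is one count line and one footnote in the table, plus the SAP wording. No visits or blood draws are added. The downside is that this row has no comparative estimate for Weeks 30-42.

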10.3 Adverse Events and Serious Adverse Events

The AE eCRF has been designed to capture all events from time of signing the informed consent through the Safety Follow-up visit. Subjects must be followed for AEs until the final required protocol visit or until all drug-related toxicities and serious adverse events (SAEs) have resolved (or are considered chronic/stable), whichever is later. All AEs will be coded by Medical Dictionary for Regulatory Activities (MedDRA) system organ class (SOC) and preferred term (PT). The MedDRA version used for reporting this study will be described in a footnote on AE related outputs.

Treatment-emergent AEs (TEAEs) are defined as AEs with an onset date on or after the start of IMP treatment. In more detail, TEAEs are all adverse events which started after start of IMP treatment; or if the event was continuous from baseline and was worsening, serious, IMP related, or resulted in death, discontinuation, interruption or reduction of IMP.

All TEAE summaries will provide the number of subjects reporting at least 1 TEAE. Tables will present the number and percentage of subjects by treatment group reporting at least 1 of the following:

- TEAE, SOC, and PT
 - TEAE leading to withdrawal of study medication, SOC, and PT
 - TEAE, severity, SOC and PT
 - Drug-related TEAE, SOC, and PT
 - Drug-related TEAE leading to withdrawal of study medication, SOC, and PT
- Treatment-emergent SAE, SOC, and PT
 - Drug-related treatment-emergent SAE, SOC, and PT
 - Fatal TEAE, SOC and PT.

A summary table will show number of subjects with at least 1 of each of the following:

- AE,
- SAE,
- TEAE,
- Severe TEAE
- TEAE leading to withdrawal of study treatment,

- Drug-related TEAE leading to withdrawal of study treatment,
- Drug-related TEAE,
- Treatment-emergent SAE,
- Drug-related treatment-emergent SAE,
- Fatal TEAE,
- All death.

TEAEs reported at least 5% of subjects in any treatment groups, and non-serious TEAEs reported at least 5% of subjects in any treatment groups will be summarized by SOC and PT for each treatment group.

TEAEs will be summarized by 1) worst severity, and 2) worst causality by SOC and PT. For each subject and each PT, the worst severity recorded will be used in the by-severity summaries. Similarly, the most conservative causality assessment (most related to treatment) will be attributed and used in the by-causality summaries. If severity or causality is missing, data will be imputed to the worst category.

A by-subject listing of all AEs will be provided. This listing will be presented by treatment group and will include center, subject identifier, age, sex, race, AE (SOC, PT, and verbatim term), flag of TEAE, study day of onset, study day of resolution, duration, severity, seriousness, relationship to the study medication, action taken, outcome and causality.

AEs of special interest (AESI) listed in [Appendix D](#) will be summarized by treatment group. The number and percentage of subjects reporting these AESI will be provided.

